10.5. Electrocardiograms

Twelve-lead electrocardiograms (ECG) will be performed at each scheduled visit specified in [Appendix 1](#) and if the patient experienced cardiac symptoms during the study drug administration. Findings of 12-lead ECG will be classified as either “Normal”, “Abnormal, Not Clinically Significant” or “Abnormal, Clinically Significant”. Any type of ECG can be performed in case of hypersensitivity.

A shift table from baseline visit to each scheduled post-baseline visit will be summarized by treatment group. Individual 12-lead results will be presented in a data listing.

10.6. Physical Examination

Physical examinations will be performed at each scheduled visit specified in [Appendix 1](#). The following body systems will be examined:

- General Appearance
- Head and Neck
- Skin
- Cardiovascular System
- Respiratory System
- Abdominal System
- Neurological System

- Musculoskeletal System
- Lymphatic System

Findings of physical examination will be classified as either “Normal”, “Abnormal, not clinically significant” or “Abnormal, clinically significant”.

The physical examination results for each body system will be summarized by treatment group and scheduled visit (including EOT). Individual physical examination results will be presented in a data listing.

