6.6.2 Sample Storage and Shipment

During the study, blood samples for PK, immunogenicity, virology and safety analyses will be collected.

Where appropriate, the serum should be transferred into a sufficient number of transfer tubes for transport to assigned testing facilities. Primary and backup samples will be shipped to the central laboratory according to the laboratory manual, and primary samples should be shipped separately from the backup samples.

Additionally, backup samples for PK and immunogenicity should be retained at the central laboratory as a backup for up to 5 years after the end of the study in case additional analysis is required. If additional analysis for PK and immunogenicity is not required, the sample will be stored at the sponsor or a designated biobank for a further 5 years (from the date the sample is transferred to the biobank) unless a specific authorization is given by the sponsor to destroy the sample. Additional tests can be conducted at the sponsor or the biobank if it is required from a regulatory or medical perspective. Details in storage and shipment will follow the laboratory manual. Virology samples will be secured at the central laboratory for analysis and backup samples will be retained. Additional tests can be conducted for virology samples with suspected resistance. The samples can be destroyed by a specific authorization of the sponsor.

7 Statistical Analysis Plan

The statistical analysis will be performed using Statistical Analysis System (SAS) software Version 9.4 or higher (SAS Institute, Inc., Cary, North Carolina, USA). The statistical methods for this study will be described in a detailed statistical analysis plan (SAP).

Changes from analyses planned in this protocol will be documented in the SAP. Any deviations from the planned analysis as described in the SAP will be justified and recorded in the CSR.

Randomization will be stratified by age (≥ 60 years vs. < 60 years), baseline comorbidities (Yes vs. No, having at least one of cardiovascular disease, chronic respiratory disease,

hypertension, diabetes mellitus, and pneumonia), region and participation in PK sub-study (Yes vs. No) in Part 1, and by age (≥ 60 years vs. < 60 years), baseline comorbidities (Yes vs. No, having at least one of cardiovascular disease, chronic respiratory disease, hypertension, diabetes mellitus, and pneumonia) and region in Part 2, respectively.

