7.8.4.4 Electrocardiogram, Physical Examination, and Vital Sign

Actual values and change from baseline for vital sign measurements will be summarized by each treatment group at each scheduled visit using descriptive statistics. Shift tables comparing the categorical investigator interpretation of 12-lead ECGs and physical examinations at each scheduled visit with those at baseline will be summarized by each treatment group.

Individual ECG results and the investigator's interpretation, physical examination findings, and vital sign measurements (including hypersensitivity monitoring) will be presented in data listings.

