11.1.3. Viral Serology for SARS-CoV-2 Antibody

Viral serology for SARS-CoV-2 antibody test with assays detecting serum antibodies against SARS-CoV-2 will be performed locally using the serum samples (if the assay is available). Viral serology for SARS-CoV-2 antibody result will be summarized on the ITTI Set by each treatment group at each scheduled visit using frequency table.

12. Changes in the Planned Analysis

- For patients who had negative result at Day 1 or missing Day 1 result of RT-qPCR, the ITTI Set will also include these patients if they are confirmed SARS-CoV-2 infection positive by Day 2 or Day 3. These patients can also be considered as infected since the virus was detected at Day 2 or Day 3.
- All expression or text regarding phenotype will be deleted in SAP since phenotype was not analyzed.

13. Reference List

International Council for Harmonisation (ICH) Assembly. ICH E9: Statistical principles for clinical trials – Step 5. 01 September 1998.

US Department of Health and Human Services. (2010). National Institutes of Health, National Cancer Institute. Common Terminology Criteria for Adverse Events (CTCAE) Version 5.0. Available from: <http://evs.nci.nih.gov/ftp1/CTCAE/About.html>.

Chan, I. S. F., and Zhang, Z. (1999). Test-Based Exact Confidence Intervals for the Difference of Two Binomial Proportions. Biometrics 55:1202–1209.

Schoenfeld, D. (1981). The asymptotic properties of nonparametric tests for comparing survival distributions. Biometrika. 68 (1): 316–319.

CDER, CBER, Multiple Endpoints in Clinical Trials. Guidance for Industry. Draft Guidance. January 2017. Available from: <https://www.fda.gov/files/drugs/published/Multiple-Endpoints-in-Clinical-Trials-Guidance-for-Industry.pdf>

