14. APPENDICES

Appendix 1: Schedule of Assessments for Part 2

Study Day (Visit windows) ⁴	Screening ¹	Treatment Period											EOT ²	Follow-Up Period ³
	-7 to 1	1	2	3	5	7	10	14 (±1)	17 (±1)	21 (±1)	28 (±3)	56 (±5)	90 (±5)	Biweekly up to 180 (±5)
Telephone Follow-Up Visit														X
Informed consent	X													
Medical history	X													
Demographics	X													
Weight, BMI and height ⁵	X	X ⁶											X	
Hepatitis B/C and HIV test (central) ⁷	X													
Serum pregnancy test ⁸	X												X	
Inclusion/exclusion criteria	X	X ⁶												
Randomization		X ⁶												
Administration of study drug⁹		X												
Nasopharyngeal swab ¹⁰														

 SARS-CoV-2 infection by sponsor-supplied rapid SARS-CoV-2 diagnostic test or RT-PCR¹¹ 	X													

 Viral shedding (central, RT-qPCR), genotyping and phenotyping of SARS-CoV-2 viral isolates (central)¹² 		X ⁶		X		X	X	X		X	X		(X) ¹³	

Study Day (Visit windows) ⁴	Screening ¹	Treatment Period											EOT ²	Follow-Up Period ³
	-7 to 1	1	2	3	5	7	10	14 (±1)	17 (±1)	21 (±1)	28 (±3)	56 (±5)	90 (±5)	Biweekly up to 180 (±5)
Telephone Follow-Up Visit														X
Patient diary ¹⁴	X	X											(X)	
SARS-CoV-2 infection related signs and symptoms assessment ¹⁵	X	X ⁶	X	X	X	X	X	X	X	X	X	X	X	X
NEWS2	X	X ⁶	X	X	X	X	X	X	X	X	X	X	X	
Immunogenicity sampling (central)		X ⁶				X		X			X	X	X	
Viral serology for SARS-CoV-2 antibody ¹⁶		X ⁶				X		X			X	X	X	
Physical Examination	X	X ⁶											X	
Clinical laboratory analyses (central) ¹⁷	X		X		X	X	X	X			X			
Vital Signs (blood pressure, heart rate, respiratory rate, SpO ₂ and body temperature) ¹⁸	X	X ⁶	X	X	X	X	X	X	X	X	X	X	X	
NYHA class assessment	X	X ⁶												
12-lead ECG ¹⁹	X	X ⁶				X		X			X			
Radiography ²⁰	X													
Hypersensitivity monitoring ²¹		X												
Disease status monitoring ²²								X						
Prior, concomitant medication ²³								X						
Adverse events monitoring ²⁴								X						

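### SAP 10.6 drops the protocol's baseline shift table for physical examination without recording the change, so the summary table can only bound how many patients became newly abnormal

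*SAP*

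**What the plan says.** Protocol 7.8.4.4 treats the two assessments together. It plans "Shift tables comparing the categorical investigator interpretation of 12-lead ECGs and physical examinations at each scheduled visit with those at baseline", summarised by treatment group. Physical examination findings are a secondary safety endpoint (Protocol 7.3.2).

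The SAP separates them. For ECG (10.5) it keeps the comparison with baseline: "A shift table from baseline visit to each scheduled post-baseline visit will be summarized by treatment group". For physical examination (10.6) the planned summary is: "The physical examination results for each body system will be summarized by treatment group and scheduled visit (including EOT"). The only other output there is patient-level: "Individual physical examination results will be presented in a data listing". Each of nine body systems is graded on a three-level scale: normal, abnormal but not clinically significant, or abnormal and clinically significant.

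The opening of Protocol section 7 sets the rule for departures: "Changes from analyses planned in this protocol will be documented in the SAP". SAP section 12 lists two. One widens the ITTI Set to patients first confirmed positive on Day 2 or Day 3. The other reads: "All expression or text regarding phenotype will be deleted in SAP since phenotype was not analyzed". Physical examination is not among them.

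The schedule (Protocol Table 11-2; SAP Appendix 1) places physical examinations at Screening, on Day 1 before dosing, and at Day 90/EOT. There is therefore one scheduled examination after dosing.

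**The concern.** A table of counts by visit gives the number abnormal before dosing and the number abnormal afterwards. It does not say whether they are the same patients. For safety, the natural question is how many patients who were normal before dosing became abnormal. A shift table answers that directly, and the protocol promised one. The population is acutely infected and symptomatic, so some baseline abnormalities may well resolve; if they do, new ones would be offset in the totals.

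The omission does not look like shorthand for a shift table. Where the SAP intends one it says so: Symptom Checklist 1 (9.4.1), urinalysis (10.2), ECG (10.5), and SARS-CoV-2 signs and symptoms (10.9). The 10.6 sentence is instead built like the pregnancy-test summary in 10.7, which is a plain count by visit. At stake are one descriptive safety output and the traceability of a departure from the protocol.

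**Working it through.** The documents state no figure on this point, so there is nothing to reproduce. The check has two parts.

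**Text comparison**

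| Item | Protocol | SAP |
|---|---|---|
| 12-lead ECG | Shift from baseline, by arm (7.8.4.4) | Shift from baseline, by arm (10.5) |
| Physical examination | Shift from baseline, by arm (7.8.4.4) | Summary by arm and visit, plus listing (10.6) |
| Record of change | Required (section 7) | Not in section 12 |

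**What counts by visit can show**

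Take n patients examined at both times, with B abnormal at baseline and E abnormal at EOT in one body system. Let N be the number newly abnormal. The number persisting is then E − N, which cannot exceed B, so N ≥ E − B. Also N cannot exceed E, nor the n − B patients who were normal at baseline. Hence

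max(0, E − B) ≤ N ≤ min(E, n − B).

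The input n = 650 is the planned number per arm (SAP 4.1). The abnormality rates are assumptions, because the documents give none. Worked case, 10% at baseline and 5% at EOT: B = 0.10 × 650 = 65; E = 0.05 × 650 = 32.5, taken as 32. The lower bound is max(0, 32 − 65) = 0 and the upper bound is min(32, 650 − 65) = min(32, 585) = 32.

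| Assumed rate, baseline then EOT | B | E | Net change | Possible N |
|---|---|---|---|---|
| 5%, 5% | 32 | 32 | 0 | 0 to 32 |
| 10%, 5% | 65 | 32 | −33 | 0 to 32 |
| 10%, 10% | 65 | 65 | 0 | 0 to 65 |
| 20%, 5% | 130 | 32 | −98 | 0 to 32 |
| 20%, 10% | 130 | 65 | −65 | 0 to 65 |

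Whenever E is no larger than B, and E does not exceed the number normal at baseline (true in every row), the table is compatible with none of the EOT abnormalities being new and with all of them being new. A shift table would give N exactly. If some patients lack the later examination, the two counts come from different sets of patients and the bounds are looser still.

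**The case against.** The strongest reply is that little is actually lost.

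- **Adverse events.** Clinically significant examination findings that meet the adverse-event definition are recorded (Protocol 6.2.9), and findings identified as adverse events go on the AE page (6.2.1.2). New or aggravated events are tabulated by arm (SAP 10.1.1).
- **Listing.** Individual results are listed, so change within a patient can be recovered.
- **Overlapping shift table.** SAP 10.9 keeps a shift table by arm for signs and symptoms, covering at least ears, nose, throat, sinuses and lungs, at many more visits than the physical examination.
- **Randomised comparison.** The table in 10.6 is by arm. The between-arm difference in E equals the difference in new abnormalities plus the difference in persisting ones. A real excess of new findings vanishes completely only if the same arm has exactly that many fewer persisting findings.
- **Latitude.** Protocol 7.8.4 allows descriptive statistics or shift tables for other safety analyses, as appropriate.

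Most of this stands, and it narrows the point. A reader might infer that new abnormalities will be hidden from the report behind resolving COVID-19 findings, or that two arms with very different numbers of new findings will look alike. The documents do not support either as an expected outcome. The data remain available by the routes above, no abnormality or resolution rates are given, and complete masking is a special case.

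Some of the point survives. Adverse-event capture does not reach a change from normal to abnormal but not clinically significant. Nor does it reach COVID-19 worsening judged unrelated to study drug, which Protocol 6.2.1.3 keeps out of AE reporting. SAP 10.9 does not name the skin, cardiovascular, abdominal, neurological, musculoskeletal or lymphatic systems. Whether its table includes Day 90 is unclear: SAP section 5 leaves EOT out of visit-based tables unless stated otherwise, and the table sentence in 10.9 excludes only the follow-up period. A listing is not the comparison by arm that was planned. The general wording in 7.8.4 does not displace the specific commitment in 7.8.4.4, nor the rule that changes be documented.

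**Conclusion.** The point holds as an undocumented mismatch between protocol and SAP in one descriptive safety table. As planned, the table in 10.6 bounds the number of newly abnormal patients without identifying it. The bound is arithmetic and needs no assumption about rates. How much it matters in practice does need such assumptions, and the documents supply none, so the size is unknown.

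The gap lies in the summary table, not in the data. It concerns mainly new abnormalities judged not clinically significant and findings attributed to unrelated COVID-19 worsening, above all in the body systems that SAP 10.9 does not name. Importance is low: no efficacy result, error rate or power figure depends on it. The change is still worth making, because physical examination is a named safety endpoint and the protocol already specified the better table.

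**What to change.** In SAP 10.6 add, for each body system and by treatment group, a shift table from baseline to the post-baseline examination, using the three existing categories (normal; abnormal, not clinically significant; abnormal, clinically significant). Baseline is the last non-missing value before dosing, as SAP 5.5 already defines it. The later examination is Day 90, or the EOT examination for patients who withdraw early; SAP 4.1 asks those patients to attend for it at their next scheduled visit. The counts by visit can stay alongside.

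If the sponsor prefers to keep counts by visit only, section 12 must record that change and give the reason.

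The cost is one SAP sentence and nine small tables. The ECG output uses the same three categories and can serve as the template. No new data are needed, and sample size, alpha and power do not change.

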10.7. Pregnancy Test

Only female patients of childbearing potential with a negative pregnancy test results can be enrolled. Serum pregnancy test will be performed for female patients with childbearing potential at each scheduled visit specified in [Appendix 1](#). However, if serum pregnancy test is not available at the study site, urine pregnancy test can be performed.

The serum (or urine) pregnancy test samples will be analyzed at the local laboratory, and will be classified as either “Negative”, “Positive” or “Indeterminate”.

The pregnancy test results will be summarized by using the number of female patients with childbearing potential as a denominator by treatment group at each scheduled visit (including EOT), displaying the number and percentage of patients. Individual pregnancy test results will be presented in a data listing.

10.8. Immunogenicity

Blood samples for immunogenicity assessments will be collected at each scheduled visit specified in [Appendix 1](#). Additional immunogenicity test will be performed if a patient experiences any immune-related AEs after the study drug administration.

The anti-drug antibody (ADA) assay will follow a three tiered approach consisting of (i) screening assay, (ii) confirmatory assay, and (iii) titration. The test outcome for the screening assay will be “Potential Positive” or “Negative”. Samples that are “Potential Positive” in the screening assay will be undergone further testing in the confirmatory assay to determine if patients are true positive. The test outcome for the confirmatory assay will be “Reactive”, “Negative” or “Not applicable (N/A)”. “Reactive” indicates a true positive test outcome and will be labeled as “Positive” in outputs, “Negative” is considered negative and “N/A” indicates the assay was negative at the screening phase of the process. Patients with a “Negative” test outcome for either screening or confirmatory assays will be considered as negative for the overall ADA assessment. For further characterization, the antibody level will be assessed by titration in confirmed positive samples.

Samples that are positive in the ADA assay will be analyzed further to conduct a neutralizing antibody (NAb) assessment. The test outcome for the screening assay will be “Positive” or “Negative”.

The results of the final ADA and the screening NAb assay at each scheduled visit will be summarized by treatment group, displaying the number and percentage of patients.

In addition, the number of patients and percentages with positive ADA and NAb conversion will be summarized. The rule of ADA and NAb conversion is as follows:

- ADA Conversion is defined as patients who reported at least one ADA positive result after study drug administration in patients who
 - Have at least one ADA result after study drug administration, and
 - Do not have any ADA positive result before study drug administration.
- NAb Conversion is defined as patients who reported at least one NAb positive result after study drug administration in patients who
 - Have at least one ADA result after study drug administration, and
 - Do not have any NAb positive result before study drug administration.

Actual values for ADA titration will be summarized by treatment group at each time point using descriptive statistics. Individual immunogenicity test results will be presented in a data listing.

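### SAP 10.8 gives no summary category to an ADA titre rise in patients already positive before dosing, and its conversion wording admits patients with no pre-dose result

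*SAP*

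**What the plan says.** SAP 10.8 sets the ADA rule in three pieces. The numerator is introduced by "ADA Conversion is defined as patients who reported at least one ADA positive result after study drug administration in patients who" meet two conditions. The first is "Have at least one ADA result after study drug administration, and" the second is "Do not have any ADA positive result before study drug administration".

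NAb conversion has a parallel rule, but its pre-dose condition concerns NAb rather than ADA: "Do not have any NAb positive result before study drug administration".

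On titre, the section says "For further characterization, the antibody level will be assessed by titration in confirmed positive samples", and the planned output is "Actual values for ADA titration will be summarized by treatment group at each time point using descriptive statistics". It asks for no change from baseline and sets no fold-rise threshold.

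Two further outputs keep all patients: "The results of the final ADA and the screening NAb assay at each scheduled visit will be summarized by treatment group", as numbers and percentages, and a listing of individual immunogenicity results. Protocol 7.8.4.6 asks only for listing and summary where appropriate. Neither document defines a treatment-emergent or treatment-boosted ADA response.

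**The concern.** A response to a biologic can appear in two ways: new antibody in a patient who had none, or a rise in antibody that was already present. The conversion rule sees only the first. Immunogenicity is a secondary safety endpoint (Protocol 7.3.2) and is named in the secondary safety objective (SAP 3.3), so a reader of the study report will want to know about both.

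The SAP treats other safety data differently. Its TEAE definition (10.1) covers worsening from baseline as well as new events. Laboratory values, vital signs and hypersensitivity monitoring are summarised as change from baseline (10.2 to 10.4), and ECG findings and infection signs as shifts (10.5, 10.9). ADA titre has neither.

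There is also a wording problem. The rule requires a post-dose result but no pre-dose result. A missing result is not a positive one, so a patient without a Day 1 sample passes the second condition. If that patient is positive later, a conversion is recorded that nobody observed.

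**Working it through.** **Step 1. What data exist.** SAP Appendix 1 schedules immunogenicity samples on Day 1 (footnoted as taken before dosing) and on Days 7, 14, 28, 56 and 90. Confirmed positives are titrated, so a patient positive on Day 1 should have a baseline titre and, if still positive, later titres to compare with it.

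**Step 2. Run each patient type through the ADA rule**, assuming at least one post-dose result.

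| Pre-dose ADA | Post-dose ADA | In numerator | In denominator |
|---|---|---|---|
| Negative | Any positive | Yes | Yes |
| Negative | All negative | No | Yes |
| Positive | Positive, titre stable | No | No |
| Positive | Positive, titre rising | No | No |
| Missing | Any positive | Yes | Yes |

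The third and fourth rows are treated alike. The fifth row is counted as conversion.

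**Step 3. Look for the fourth row in the other outputs.**
- By-visit ADA results: the patient is positive before and after, exactly like a stable patient.
- By-visit titre: these are group actual values in whoever is positive at that visit. The contributing patients can change between visits, so new low-titre positives can hide a rise in the others.
- NAb conversion: it captures such a patient only if NAb goes from not positive to positive, which is a different event from a titre rise.
- Listing: the rise is visible, patient by patient.

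SAP Section 5 also leaves unscheduled and EOT visits out of visit-based tables unless otherwise specified. Sections 10.6 and 10.7 add EOT explicitly and 10.8 does not. On a plain reading, Day 90 titres are therefore outside the by-visit summaries too.

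**Step 4. Size.** The documents give no immunogenicity rate, so there is no planned figure to reproduce. Define:
- b = share of patients ADA positive before dosing
- c = conversion rate in pre-dose negatives
- r = share of pre-dose positives whose titre rises

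Take 650 per arm (SAP 4.1), all evaluable and none missing a pre-dose result. Then:
- SAP conversion percentage = c
- New plus boosted percentage = (1 − b)c + br
- Difference = b(r − c)
- Boosted patients per arm outside the conversion count = 650 × b × r

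The values of b, c and r below are assumptions, drawn from a grid of b 1–10%, c 1–5% and r 0–50%.

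| b | c | r | Boosted, uncounted | SAP % | New plus boosted % | Difference (points) |
|---|---|---|---|---|---|---|
| 1% | 5% | 20% | 1.3 | 5.00 | 5.15 | +0.15 |
| 5% | 5% | 20% | 6.5 | 5.00 | 5.75 | +0.75 |
| 10% | 1% | 50% | 32.5 | 1.00 | 5.90 | +4.90 |
| 10% | 5% | 5% | 3.25 | 5.00 | 5.00 | 0.00 |
| 10% | 5% | 0% | 0 | 5.00 | 4.50 | −0.50 |

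The last three rows show the difference positive when r > c, zero when r = c and negative when r < c. The third and last rows are the extremes of the grid.

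**The case against.** The best defence is that the SAP calls this measure conversion and never presents it as total treatment-emergent immunogenicity. Conversion from negative to positive can be observed only in patients who start negative, so that denominator is coherent. This stands: the rule is sound for what it names, and the gap is that nothing beside it reports boosting.

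A reader might infer that pre-dose positives vanish from the immunogenicity reporting. They do not. They stay in the by-visit ADA and NAb tables, the titre summaries and the listing. A patient who is ADA positive but not NAb positive before dosing can still count towards NAb conversion. What is missing is narrower: a summary that separates a rising titre from a stable one.

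A reader might also infer that the rule understates the immunogenicity rate. The documents do not support that. The excluded patients leave the denominator as well, and the sign of b(r − c) depends on rates that neither document gives. Only the count of new plus boosted cases has a fixed direction: it is too low or, if nobody is boosted, correct.

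On missing baselines, the Day 1 sample is scheduled for everyone, so few patients should be affected. This bears on the size of the problem but does not repair the wording. It is also fair that neither document contains a fold-rise threshold, so any value is a proposal.

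**Conclusion.** The point holds as a small gap in a descriptive safety summary. A post-dose titre rise in a patient who was ADA positive before dosing belongs to no summary category and can be found only in the individual listing. The conversion count therefore omits any boosted cases: 0 to 32.5 per arm over the assumed grid. That range rests on assumed pre-dose prevalence and boost shares and on all 650 patients per arm being evaluable. The percentage could move by −0.50 to +4.90 points over the same grid, so neither the size nor the direction of that effect is established.

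Separately, and regardless of those assumptions, the wording counts a patient with no pre-dose result and a post-dose positive as a converter. The documents do not allow that number to be estimated.

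No hypothesis test depends on this analysis, and the primary and key secondary efficacy conclusions are unaffected. It is an inexpensive improvement rather than a defect that threatens the trial.

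**What to change.** Amend SAP 10.8 before unblinding as follows.

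1. **Conversion (induced).** Keep ADA conversion, but require a non-missing, negative pre-dose ADA result and at least one post-dose result.
2. **Boosted.** Add patients with a positive pre-dose result whose post-dose titre rises by at least a fold-change fixed before unblinding, for example 4-fold or the assay's validated step. The denominator is pre-dose positives with at least one post-dose result.
3. **Combined.** Report induced, boosted and combined counts by arm. The combined denominator is patients with a pre-dose result and at least one post-dose result.
4. **No pre-dose result.** Show these patients on a separate line, not as converters.

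The cost is SAP wording and one extra table. The samples are already scheduled and confirmed positives are already titrated, so no new sampling is needed. The downside is that the reported count of immunogenicity cases may be slightly higher.
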